Accordingly, the demand for next-generation P2Y12 antagonists has continued, and according to a paper published in 2007, clopidogrel and prasugrel patient responses and platelet activity inhibition were compared before percutaneous coronary intervention [1]. Reportedly, the platelet aggregation inhibitory effect is remarkably high. Choi et al. revealed the efficacy of prasugrel in coil embolization of cerebral aneurysms with stent insertion; the incidence of thromboembolism was significantly lower in the prasugrel group than in the clopidogrel group (0.9% vs. 6.4%; $P = 0.01$), and the bleeding risk was reported to be similar (0.5% vs. 2.2%; $P = 0.22$) [2,3]. However, these recent studies are based on single-center retrospective data; therefore, there is a limit to the level of evidence.

This study aimed to compare the safety and usefulness of prasugrel vs. clopidogrel in patients scheduled to undergo stent or diverter treatment for unruptured cerebral aneurysms.

Specific Aim and Hypothesis

The primary aim of the present study was to investigate the effect of prasugrel in patients undergoing neurointerventional treatment for UIAs (i.e., stent-assisted coiling or flow diverter insertion). The prasugrel and clopidogrel groups were compared to elucidate their safety (hemorrhagic complications) and efficacy (thromboembolic complications) in the periprocedural period. In the present study, we hypothesized that prasugrel has a preventive effect that is not inferior to that of clopidogrel in any treatment group.

Research Design and Methods

Research Design

Patients who visited the outpatient department of neurosurgery at multiple institutions (Severance Hospital, Gangnam Severance Hospital, Yongin Severance Hospital, Ewha Womans University Seoul Hospital, Bucheon St. Mary's Hospital, and International St. Mary's Hospital) were screened to participate in the present research. After following the study protocol, the participants were divided into the prasugrel and clopidogrel groups by 1:1 randomization.

- Detailed information of the study protocol
- 1) After patients with UIAs were hospitalized, baseline characteristics were obtained, and blood tests, including renal function test (glomerular filtration rate [GFR]), liver function test (aspartate aminotransferase [AST]/alanine aminotransferase [ALT]), and pregnancy test, were performed.

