Demographic data	O	-	O					
Medical History	O	-	O					
Vital sign	O	-	O		O	O	O	O
Neurological examination	O	-	O		O	O	O	O
Aneurysm data	O	-						
Radiologic data	O	-			O	O		
Medication compliance	-	-	O					O
VerifyNow test	-	-	-	O				

Study Population

At the time of initial admission for pretreatment examination, patients were screened based on their medical history, vital sign evaluation, and laboratory tests (hematological tests, biochemical tests, urinalysis, and pregnancy test). Detailed inclusion and exclusion criteria of the present study were as follows:

- **Inclusion Criteria**

- Patients aged between 19 and 75 years
- Aneurysms without any evidence of rupture on an intracranial imaging study within the last 6 months
- Planned treatment with coil embolization with stent insertion or flow diverter insertion
- If the patient itself consented to this study

● **Exclusion Criteria**

- History of acute ischemic stroke or transient ischemic attack
- Any intracranial hemorrhage except subarachnoid hemorrhage due to aneurysm rupture within the last 3 months
- Concurrent treatment other than endovascular procedures (e.g., open craniotomy and microsurgical clipping)
- Contraindications to iodine contrast agents
- Already taking antiplatelet or antithrombotic drugs other than aspirin
- Hypersensitivity to aspirin, prasugrel, or clopidogrel
- Cardiac arrhythmia that should be needed to take anticoagulants
- Pregnant or lactating women
- Chronic kidney disease (GFR <60)
- Patients with chronic liver disease who had at least 100 IU/L of either AST/ALT in the liver function test
- Patients with pathological active bleeding, as seen in peptic ulcer
- Patients with genetic problems such as galactose intolerance, Lapp lactase deficiency, or glucose-galactose malabsorption because they contain lactose
- Patients continuously taking non-steroidal anti-inflammatory drugs and cyclooxygenase-2 inhibitors
- Patients requiring concomitant administration of ≥ 15 mg methotrexate for a week
- If the case was difficult to follow up after treatment

Randomization

Randomization was conducted using the randomization program provided by the Seoul National University Hospital Biomedical Research Institute (<http://mrcc.snu.ac.kr>) and managed by a third party to ensure that the researchers were blinded to the assignments.

Study Endpoints

The primary endpoint was intraprocedural thromboembolic complications or

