postprocedural ischemic stroke or death. The detailed information is as follows:

- A thromboembolism detected during the neurointerventional procedure
- Transient ischemic attack, ischemic stroke, or death with evidence of infarction on diffusion-weighted imaging, occurring within 30 days after the procedure

The secondary endpoints were postprocedural stroke and diffusion-restricted lesions on diffusion-weighted MRI. Another secondary endpoint was the preprocedural platelet function test value and its adjustment ratio. The details are as follows:

- Ischemic stroke in the relevant arterial territory within 30 days after the procedure
- Any stroke, including ischemic and hemorrhagic strokes, within 30 days after the procedure
- Disabling or fatal stroke within 30 days after the procedure
- Diffusion-restricted lesion detected on the 7-day postprocedural MRI

The safety endpoints were bleeding related to P2Y12 antagonists, including any bleeding within 30 days or major bleeding. Bleeding criteria followed the PLATelet inhibition and patient Outcomes bleeding criteria [4,5].

- Major bleeding criteria
 - ✓ Fatal bleeding (bleeding that directly results in death within 7 days)
 - ✓ Intracranial bleeding
 - ✓ Intrapericardial bleeding with cardiac tamponade
 - ✓ Hypovolemic shock or severe hypotension due to bleeding, requiring pressors or surgery
 - ✓ A decline in the hemoglobin level of ≥ 5.0 g/dL
 - ✓ Need for transfusion of at least 4 units of red blood cells
- Other major bleeding criteria
 - ✓ Bleeding that led to clinically significant disability
 - ✓ Decline in hemoglobin level of ≥ 3.0 g/dL but < 5.0 g/dL
 - ✓ Need for transfusion of at least 2-3 units of red blood cells
- Minor bleeding criteria
 - ✓ Any bleeding requiring medical intervention but not meeting the criteria for major bleeding

Determination of the Sample Size

Given the hypothesis of the present study, we used a two-proportion Z-test with pooled variance and set the significance level at 0.05, power = 0.8.

In previous retrospective studies, intraprocedural thromboembolism occurred in the prasugrel group (0.009) and the clopidogrel group (0.064), with a -0.055 difference in the ratio of any stroke and death during the 30-day treatment. A total of 182 samples were required to prove significance at 80% for each group. Considering the 10% dropout rate, 203 patients were required per group, with a total of 406 patients.

Statistical Analysis

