Statistical analysis was performed using SAS®(25) version 9.4 or later versions. All the efficacy analyses were based on the intention-to-treat principle. For comparison of all study endpoints (primary, secondary, and safety), 1) ratio data were analyzed using Pearson's chi-square test and 2) continuous variable comparison was analyzed using an independent two-sample t-test. All statistical tests were based on a two-tailed test with a significance level of 5%, and the safety analysis presented observations without correction for missing values.

- Baseline characteristics

Continuous variables are expressed as the mean \pm standard deviation. Categorical and continuous variables of the baseline characteristics were compared and analyzed using the chi-square or Fisher's exact test and Student's t-test.

- All endpoints

For comparison of all endpoints (primary, secondary, and safety) in the two groups, 1) ratio-type data were analyzed using Pearson's chi-square test and 2) continuous variable comparison was analyzed using an independent two-sample t-test. Statistical significance was set at $P < 0.05$.

- Exploratory subgroup analyses

For the following pre-defined subgroups, subgroup analysis was performed to determine the difference between the overall primary and secondary endpoints.

- ✓ Previous major cardio-cerebrovascular accident
- ✓ Clopidogrel responsiveness (hyporesponder, $PRU \geq 220$; responder, $PRU < 220$)

- ✓ Cerebral aneurysm size in the stent group (<5 mm or \geq 5 mm)
- ✓ Parent artery diameter (mean diameter <2.5 mm or ≥2.5 mm)
- ✓ Procedure (stent-assisted coiling, flow-diverter)
- ✓ Occlusion grade (Roy-Raymond classification)

The difference between the test and control groups according to subgroup followed the regression model with interaction.

Possible Risks and Benefits

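### The DWI-lesion endpoint is compared with a crude chi-square; prespecified baseline adjustment could add power at almost no cost

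*Combined protocol and SAP*

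**What the plan says.** Statistical Analysis, under the item on all endpoints, sets a single rule "For comparison of all endpoints (primary, secondary, and safety) in the two groups": Pearson's chi-square for proportions and an independent t-test for continuous measures. It names no covariate and no adjusted sensitivity analysis. Regression appears only for the exploratory subgroups, with an interaction term. Those subgroups include procedure (stent-assisted coiling or flow diverter), aneurysm size within the stent group, and "Parent artery diameter (mean diameter <2.5 mm or ≥2.5 mm"). Age is not among them.

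The Time table marks demographic data, "Aneurysm data" and radiologic data at screening but does not list the variables in those rows. Planned procedure and age are also eligibility items. Patients are allocated "by 1:1 randomization", and the Randomization section describes no stratification factor.

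The sample size rests on the primary endpoint alone (Determination of the Sample Size). No power, lesion rate or PRU standard deviation is given for the secondary endpoints.

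**The concern.** The plan collects, or very likely collects, baseline factors that could plausibly predict a diffusion-restricted lesion, yet uses them only in exploratory models. When a factor predicts outcome, a crude comparison leaves explainable variation in the error term. For an endpoint with a reasonable number of events, prespecified adjustment recovers some of that.

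The DWI lesion is the natural candidate. It is expected to be far more frequent than the primary endpoint, for which the planning rates imply about 13 events. What is at stake is power on one secondary endpoint. There is also a prespecification benefit: the plan compares baseline characteristics between arms but does not say how an imbalance would be used, so any later adjustment would be post hoc.

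**Working it through.** **1. The plan's own figure.** The plan states "we used a two-proportion Z-test with pooled variance and set the significance level at 0.05, power = 0.8", with rates of 0.064 and 0.009 and two-sided testing.

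n = [1.960·√(2·0.0365·0.9635) + 0.842·√(0.064·0.936 + 0.009·0.991)]² / 0.055² = (0.520 + 0.221)² / 0.003025, which rounds up to 182. Then 182/0.9 = 202.2, giving 203.

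Both stated figures reproduce, and the present point does not touch them.

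**2. Crude power for the DWI lesion at assumed rates.** Take 45% versus 33% (assumed) and 182 per arm. The pooled SE is √(0.39·0.61·2/182) = 0.0511. The unpooled SE is √((0.45·0.55 + 0.33·0.67)/182) = 0.0507. Power = Φ((0.12 − 1.960·0.0511)/0.0507) ≈ 65%. There is room to gain.

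**3. Effect of adjustment, by simulation.** The first set uses 182 per arm and 4,000 trials per row. It compares the chi-square with a logistic model containing treatment and four equally weighted, independent baseline covariates. The treatment effect is set for about 80% crude power.

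| Assumed rates (control vs prasugrel) | Outcome variance explained | Crude power | Adjusted power |
|---|---|---|---|
| 30% vs 17.5% | 0% | 79.0% | 79.0% |
| | 4.8% | 80.0% | 80.7% |
| | 15.7% | 80.4% | 86.2% |
| | 27.5% | 80.2% | 89.5% |
| 50% vs 35.5% | 0% | 80.0% | 80.0% |
| | 5.6% | 80.1% | 82.4% |
| | 17.3% | 78.7% | 85.8% |
| | 29.3% | 80.2% | 92.4% |
| 60% vs 45.4% | 0% | 80.4% | 79.5% |
| | 5.4% | 80.0% | 81.3% |
| | 16.9% | 80.1% | 86.4% |
| | 28.9% | 79.8% | 90.8% |

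The simulation SE of each power is about √(0.8·0.2/4000) = 0.6 points.

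A second set simulated the estimator recommended below, a standardised risk difference from a four-covariate logistic model, at 182 per arm and an assumed 45% control rate. Type I error was 4.3–5.4%. Useless covariates cost no power, and the gains were about 2, 7 and 13 points for weak, moderate and strong predictors.

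A third set used 203 per arm, about 45% versus 33%, and a linear-probability model with procedure, size and age. Power went from 74% to 75%, 68% to 73% and 66% to 75%. Its adjusted type I error was 5.7% (SE 0.35), about two SEs above 5%, so its 1-point weak-predictor gain should be read as none.

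Together: about 0–2 points (weak), 5–7 (moderate), 9–13 (strong), and a loss of at most about 1 point if the covariates are not prognostic.

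**4. The same idea applied to PRU.** With 182 per arm, 80% crude power needs a standardised effect of 2.802·√(2/182) = 0.294. Replacing the SD by √(1 − R²) gives 80.4%, 80.8% and 82.0% at R² = 0.01, 0.02 and 0.05 (assumed). With a standardised effect of 0.5, crude power is already Φ(0.5/0.1048 − 1.960) = 99.7%.

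**5. The same idea applied to the primary endpoint.** Expected events are 182·(0.064 + 0.009) = 13.3. In simulation at the planning rates, a four-covariate logistic Wald test had 60–65% power against about 85% for the chi-square.

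**The case against.** - **The crude test is valid.** This stands. Under randomisation its type I error already allows for chance imbalance. A reader might infer that the comparison is biased or unsafe because device type can differ between arms; the documents do not support that. The SD of the chance difference in flow-diverter share is √(2f(1 − f)/203), or 4–5 points for an assumed f of 0.2–0.5. Even with an assumed 20-point device difference in lesion risk, the contrast shifts by 0.20·0.05 = 1 point, against a crude standard error of about 4.8 points.
- **The size of the gain is assumed.** This stands. A place in the subgroup list suggests possible effect modification and does not establish prognosis. The list also contains on-treatment PRU and occlusion grade, which are not baseline factors.
- **Collection at screening is partly inferred.** This also stands. Aneurysm size and artery diameter are not itemised in the schedule; their presence is read from generic rows and the subgroup list.
- **Adjustment might inflate type I error.** This applies to the linear-probability simulation. It does not apply to the standardised logistic estimator, whose simulated error was 4.3–5.4%.

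**Conclusion.** The point holds for the DWI lesion only, as an inexpensive efficiency gain of low priority. The expected benefit runs from nothing to about 13 points of power, depending on a prognostic strength that the documents do not give. The downside is about 1 point at most. These figures assume lesion rates near 45% versus 33% (30–60% in the control arm was also examined), about 182 evaluable patients per arm, and independent covariates.

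Two stronger readings are tempting and are not supported:

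- **That PRU loses power in the same way.** VerifyNow is scheduled once, the day before the procedure and on study drug, so there is no pre-treatment value to adjust for. Nothing in the documents links procedure, aneurysm size or artery diameter to platelet reactivity. Age is at most an unquantified predictor.
- **That the primary, stroke and bleeding tests should change.** With about 13 primary events, multi-covariate adjustment lost power in simulation. No benefit has been shown for a stratified test. The planned chi-square matches the test behind the sample size, where "A total of 182 samples were required to prove significance at 80% for each group".

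**What to change.** Before database lock, prespecify for the DWI lesion a standardised risk difference from a logistic model with treatment, planned procedure, aneurysm size, parent-artery diameter and age. Use a robust or influence-function standard error. Keep the crude chi-square as the supporting analysis. Use the planned procedure, not the one performed, and state the form of each covariate. Confirm that size and diameter are recorded before randomisation, and state how missing covariate values are handled.

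Leave the PRU analysis as it is, and add no multi-covariate adjustment to the primary, stroke or bleeding endpoints.

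The cost is a paragraph of SAP text and a few lines of SAS. The one constraint is that the covariates must be fixed in advance. No change to the sample size is needed.

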- 2) Cerebral angiography was performed, and detailed consent was obtained after the study protocol was explained to the participants who met the selection criteria.
- 3) Using a randomization program, the test group (203 patients; aspirin 100 mg + prasugrel 5 mg) and the control group (203 patients; aspirin 100 mg + clopidogrel 75 mg) were classified.
- 4) The above drugs were prescribed according to the assigned group and taken 5 days before the procedure.
- 5) The patients were hospitalized 2 days before the procedure, and whether the drug was taken was checked immediately after hospitalization (if the drug was not taken properly, the patient was excluded from the study).

6) The platelet function test (VerifyNow assay; Accumetrics, San Diego, California, USA) was performed a day before the procedure to check the clopidogrel responsibility and adjust the drug according to the result.

P2Y12 reaction units (PRU) <220

- Clopidogrel group: aspirin 100 mg + clopidogrel 75 mg
- Prasugrel group: aspirin 100 mg + prasugrel 5 mg

PRU ≥220

- Clopidogrel group: aspirin 100 mg + clopidogrel 75 mg + cilostazol 100 mg
- Prasugrel group: aspirin 100 mg + prasugrel 5 mg + prasugrel 5 mg

The morning on the day of the procedure, after administering the drug at the adjusted dose, the planned intracerebrovascular procedure was performed.

7) Brain magnetic resonance imaging (MRI) was performed within 7 days from the day of the procedure (i.e., from the day of the procedure to 1 week after the procedure, and it varied depending on the clinical situation).

8) If there were no neurological abnormalities or complications, the patient was discharged with discharge medication on the next day following the procedure.

- Clopidogrel group: aspirin 100 mg + clopidogrel 75 mg
- Prasugrel group: aspirin 100 mg + prasugrel 5 mg

9) On postoperative day 30 (30-35 days after the procedure), the patient's clinical courses and complications were assessed. If there were no specific findings, the drug was changed to aspirin 100 mg + clopidogrel 75 mg in both groups.

- Time table

Procedure	Screening	Pre-medication	Admission	Medication adjustment	Treatment	Follow-up 1 (MR)	Follow-up 2	Follow-up 3
Time period	Day -60 ~ -6	Day -5 (out-patient)	Day -2 (in-patient)	Day -1 (in-patient)	Day 0 (in-patient)	Day 1 (in-patient)	Day 2 (discharge)	Day 30
Visit window	-	0~± 1 day	0~± 1 day	0 ~+1 day	-	0~+1 day	0~+3 days	0~± 5 days
Informed consent	O	-						
Inclusion/Exclusion Criteria	O	-						

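### The clopidogrel-responsiveness subgroup is defined by a PRU value measured after randomisation on the assigned drug, so arm comparisons by PRU category are not randomised and should be descriptive only

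*Combined protocol and SAP*

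**What the plan says.** The document is a combined protocol and SAP. The sequence of events comes from the numbered study steps under Research Design and from the Time table.

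- **Step 3:** patients are randomised, 203 per arm.
- **Step 4:** "The above drugs were prescribed according to the assigned group and taken 5 days before the procedure".
- **Step 6:** the platelet function test "was performed a day before the procedure to check the clopidogrel responsibility and adjust the drug according to the result". At PRU ≥220 the regimens become "Clopidogrel group: aspirin 100 mg + clopidogrel 75 mg + cilostazol 100 mg" and "Prasugrel group: aspirin 100 mg + prasugrel 5 mg + prasugrel 5 mg". Below 220 each arm keeps its assigned regimen.
- **Step 9:** at Day 30, absent specific findings, "the drug was changed to aspirin 100 mg + clopidogrel 75 mg in both groups".
- **Time table:** the row "VerifyNow test" has a single mark, in the Day -1 column.
- **Exclusion Criteria:** "Already taking antiplatelet or antithrombotic drugs other than aspirin" rules a patient out at entry.
- **Study Endpoints:** the platelet function value before the procedure is itself a secondary endpoint.
- **Exploratory subgroup analyses:** the pre-defined list includes the item "Clopidogrel responsiveness (hyporesponder", with hyporesponders at PRU ≥220 and responders below 220. Differences between arms by subgroup are to be assessed by regression with an interaction term. Nothing marks this item as a post-randomisation variable or limits it to description.

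**The concern.** A subgroup analysis supports a statement about effect modification when the subgroup is fixed before treatment can influence it. Randomisation then balances the arms within each subgroup. Here the subgroup variable is measured on the assigned drug. If the two drugs suppress platelets to different degrees, the prasugrel patients at PRU ≥220 are a different, more selected group than the clopidogrel patients at PRU ≥220, and the same holds below 220.

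The label adds to the problem. A reader would take the result as showing whether prasugrel works differently in clopidogrel hyporesponders. The design cannot show that, because no prasugrel patient is tested on clopidogrel.

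**Working it through.** **1. Order of events.** Randomisation (step 3) comes before the first dose of assigned drug on Day -5 (step 4), which comes before the PRU test on Day -1 (step 6). No test is scheduled before randomisation, on a common drug, or after the Day 30 change to clopidogrel. Patients already on a non-aspirin antiplatelet are excluded at entry, and steps 3 to 6 give the prasugrel arm no clopidogrel before the test. So PRU category means response to clopidogrel in one arm and response to prasugrel in the other.

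**2. Can assignment move the variable?** Possible Risks and Benefits reports less drug resistance on prasugrel and expects a stronger effect. It does not name PRU, but a shift in PRU is the natural reading, and PRU is compared between arms as a secondary endpoint. The same variable therefore serves as both outcome and effect modifier.

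**3. What happens at PRU ≥220.** The two arms receive different regimen changes before the procedure. Event rates in that category reflect the adjusted regimens as well as the drugs first assigned.

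**4. The plan's own figure.** The stated sample size reproduces. The inputs are 0.009 and 0.064 (mean 0.0365, difference 0.055), two-sided 5%, 80% power and pooled variance:

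n = [1.960·√(2·0.0365·0.9635) + 0.842·√(0.009·0.991 + 0.064·0.936)]² / 0.055² = (0.520 + 0.221)² / 0.003025 ≈ 181.3, rounded up to 182.

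182/0.9 = 202.2, rounded up to 203 per arm. Nothing in this concern changes it.

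**5. Illustration of the size.** Every input here except 203 per arm and the two event rates is an assumption.

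- Latent risk Z ~ N(0,1), with logit P(event) = a + 0.7Z in both arms, so the drug has no effect. The constant a is solved to give 3.65% overall, the mean of 0.9% and 6.4%.
- Latent PRU has correlation ρ with Z, and the cut-off is set in each arm to give the stated share at PRU ≥220.
- Mean Z above the cut-off is ρ·φ(c)/share, where c is the normal quantile for that share. With shares of 40% (clopidogrel) and 10% (prasugrel), this is 0.29 against 0.53 SD at ρ = 0.3, and 0.68 against 1.23 SD at ρ = 0.7.
- Category sizes at PRU ≥220 are 203 × 0.30 to 0.40 = 61 to 81 on clopidogrel and 203 × 0.10 to 0.20 = 20 to 41 on prasugrel.

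Risk ratios (RR) are prasugrel over clopidogrel; the true value is 1. Expected events are in the same order.

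| Share ≥220, clop./pras. | ρ | RR, PRU <220 | RR, PRU ≥220 | Ratio of RRs (≥220 to <220) | Expected events at ≥220, pras./clop. |
|---|---|---|---|---|---|
| 40%/10% | 0.3 | 1.10 | 1.16 | 1.06 | 1.03/3.54 |
| 40%/20% | 0.3 | 1.06 | 1.09 | 1.02 | 1.92/3.54 |
| 30%/10% | 0.3 | 1.07 | 1.12 | 1.05 | 1.03/2.76 |
| 40%/10% | 0.7 | 1.27 | 1.41 | 1.10 | 1.52/4.32 |
| 40%/20% | 0.7 | 1.17 | 1.21 | 1.03 | 2.61/4.32 |
| 30%/10% | 0.7 | 1.18 | 1.29 | 1.10 | 1.52/3.52 |

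For example, at 40%/10% and ρ = 0.7: (1.52/20.3)/(4.32/81.2) = 7.49%/5.32% = 1.41.

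**6. Test behaviour** (200,000 simulated trials per scenario, 203 per arm, nominal two-sided 5%):

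| Test | ρ = 0 | ρ = 0.3 | ρ = 0.7 |
|---|---|---|---|
| Pearson, PRU <220 | 4.8–4.9% | 4.8–4.9% | 4.8–5.3% |
| Pearson, PRU ≥220 | 3.8–4.8% | 4.6–5.9% | 6.0–8.7% |
| Interaction (log-odds, 0.5 added per cell) | not run | 2.2–3.1% | 2.5–3.5% |

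False positives rise little, and noise in such small cells exceeds the bias.

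**7. A second model.** With risk = expit(-3.0 + 0.7U), PRU = arm mean + 60U, clopidogrel mean 200 and prasugrel means of 190, 160 and 130, risk at PRU ≥220 is 9.8% on clopidogrel against 10.5%, 13.1% and 16.6% on prasugrel. Below 220 it is 3.5% against 3.7%, 4.4% and 5.0%. The direction is the same, and the gap grows with the drug's effect on PRU.

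**The case against.** The strongest reply is that this is one of six exploratory subgroups, and that the planned quantity is the interaction. On the figures above, the interaction is barely biased and its test rejects below the nominal level. The larger figures (1.41 and 8.7%) come from one extreme scenario, and 8.7% is for a within-category Pearson test that the plan does not clearly call for. Relabelling with a caveat might therefore be enough, particularly as occlusion grade is also determined after treatment and its removal is not proposed.

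Several of these points stand. The statistical distortion is small, and the concern is limited to one exploratory item. Only the drug's possible influence on PRU breaks exchangeability. The arm-specific regimen change alters what is being compared, and PRU being an endpoint does not by itself undo randomisation. The expected PRU shift is inferred. The illustration leaves out the regimen change and assumes the same PRU-risk correlation on both drugs, so its direction at PRU ≥220 is conditional.

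None of this rescues the analysis. The exploratory heading speaks to strength of evidence and does not make the categories comparable between arms. A small bias in the interaction does not help when the question in the label concerns a quantity never measured in one arm. If the subgroup was meant for clopidogrel patients only, no between-arm interaction could be estimated, and the text would still need correcting.

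**Conclusion.** The concern holds. The category is a post-randomisation, on-treatment measurement with a different meaning in each arm. Arm comparisons by PRU category, including the planned interaction, are not protected by randomisation and cannot be read as effect modification by clopidogrel response. This conclusion rests on the documented order of events and on the assigned drug being able to change PRU; it does not depend on the illustration.

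The true size of the bias is unknown, because the documents give neither a PRU distribution nor a PRU-risk correlation. Under the stated assumptions the spurious within-category risk ratio is 1.06 to 1.27 below 220 and 1.09 to 1.41 at or above it, with little inflation of false positives. This is a matter of interpretation that should be corrected. It does not threaten the trial's main result.

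**What to change.** - Relabel the variable on-treatment PRU category.
- Remove it from the list of treatment-by-subgroup interactions.
- Report PRU by arm as the secondary endpoint it already is.
- Report event counts and rates by PRU category within each arm, descriptively, with no between-arm test inside categories.
- State that PRU was measured on the assigned drug, and that rates at PRU ≥220 also reflect the arm-specific regimen change made before the procedure.
- Add a note that occlusion grade is also a post-procedure result and needs the same caution in interpretation; its removal is not proposed.

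The cost is a few sentences of SAP wording, with no new data. One exploratory between-arm comparison is lost. In the illustration it would rest on about 1.0 to 2.6 expected prasugrel events at PRU ≥220, so little information goes with it. If results have already been analysed, the change should be dated and recorded as such.

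### Occlusion grade is a result of the procedure, so the planned treatment-by-grade interaction cannot be read as effect modification; report the grade descriptively by arm

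*Combined protocol and SAP*

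**What the plan says.** Under Statistical Analysis, Exploratory subgroup analyses, the plan states: "For the following pre-defined subgroups, subgroup analysis was performed to determine the difference between the overall primary and secondary endpoints". One entry in the list is "Occlusion grade (Roy-Raymond classification", another is "Procedure (stent-assisted coiling, flow-diverter". The method is given in one sentence: "The difference between the test and control groups according to subgroup followed the regression model with interaction". No regression type or effect scale is named.

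Three other places fix the timing:

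- **Inclusion Criteria:** "Planned treatment with coil embolization with stent insertion or flow diverter insertion". At entry there is no treatment result to grade.
- **Research Design, study protocol step 4:** "The above drugs were prescribed according to the assigned group and taken 5 days before the procedure".
- **Study Endpoints, primary endpoint:** the first component is "A thromboembolism detected during the neurointerventional procedure". The second covers transient ischaemic attack, ischaemic stroke or death, "occurring within 30 days after the procedure".

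The time table collects aneurysm data at screening only, and radiologic data at screening, Day 0 and Day 1. It does not say when occlusion is graded. Nothing limits the subgroups to baseline variables, marks this one as post-randomisation, or gives a method for a subgroup formed after randomisation.

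**The concern.** A subgroup analysis asks whether the drug effect differs between kinds of patient. Randomisation supports that question only if the subgroup is fixed before treatment can act on it. Occlusion grade describes how far the aneurysm is closed once the device is in place. It may depend on the assigned drug, on the course of the procedure, and on a thromboembolism during it.

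Splitting patients by such a variable can sort events into one stratum, and can make the two arms within a stratum differ in prognosis. A treatment-by-grade interaction could then appear although the drug acts alike in everyone. Because the list is called pre-defined, readers may give such a result more weight than it can bear.

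**Working it through.** **1. The plan's own figure.** Inputs from Determination of the Sample Size: 0.009 and 0.064, two-sided 5%, power 80%, pooled variance. With mean rate 0.0365:

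n = [1.960·√(2·0.0365·0.9635) + 0.842·√(0.009·0.991 + 0.064·0.936)]² / 0.055² = (0.520 + 0.221)² / 0.003025 = 181.3 to 181.5, depending on rounding, so 182 per group. Then 182/0.9 = 202.2, so 203.

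Both stated figures reproduce. Expected events at 203 per arm are 203·0.009 = 1.8 and 203·0.064 = 13.0, about 15 in all.

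**2. Order of events.** Randomisation, then study drug about five days before the procedure, then the procedure (with any intraprocedural thromboembolism), then the grade. Strokes, TIAs or deaths up to Day 30 may come after the grade.

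**3. Formula.** Take two grades, incomplete and complete; this is a simplification, as the plan gives no cut-points. Let q0 and q1 be the probabilities of incomplete occlusion without and with an event. By Bayes' rule:

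- OR within incomplete = true OR × (q1/q0, prasugrel) / (q1/q0, clopidogrel)
- OR within complete = the same with 1−q1 and 1−q0

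If q0 and q1 are the same in both arms, the factor is 1 and the odds ratio is undisturbed. The risk difference is not. All grade probabilities below are assumptions.

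**4. The event shifts the grade equally in both arms.** Assume 30% difficult anatomy; control risk 12% in difficult and 4% in other anatomy (average 0.3·12 + 0.7·4 = 6.4%, the plan's clopidogrel rate); true risk ratio 0.5 for every patient; incomplete occlusion without an event 50% and 30%, and 30 points higher after an event.

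| | Incomplete | Complete |
|---|---|---|
| Control risk | 0.0456/0.3792 = 12.0% | 0.0184/0.6208 = 3.0% |
| Prasugrel risk | 0.0228/0.3696 = 6.2% | 0.0092/0.6304 = 1.5% |
| Risk difference | -5.9 points | -1.5 points |
| Risk ratio | 0.51 | 0.49 |
| Odds ratio | 0.481 | 0.485 |

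If the event does not affect the grade, the differences are -3.7 and -2.9 points, from anatomy alone.

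With the plan's rates (0.009, 0.064), one anatomy type and q0 = 30%, the true difference is -5.5 points and the odds ratio is 0.133 in both grades throughout:

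| q1 | Incomplete | Complete |
|---|---|---|
| 50% | -8.7 points | -4.0 points |
| 70% | -11.7 points | -2.5 points |
| 90% | -14.4 points | -0.8 points |

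**5. The grade also depends on arm.** No drug effect on the event: 0.064 in both arms, true OR 1.00.

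| Assumed incomplete occlusion (prasugrel vs clopidogrel) | OR, incomplete | OR, complete |
|---|---|---|
| Without event 20% vs 40%; after event 70% in both | (0.7/0.2)/(0.7/0.4) = 2.00 | (0.3/0.8)/(0.3/0.6) = 0.75 |
| Without event 20% vs 30%; after event 70% in both | 1.50 | 0.88 |
| Without event 30% in both; after event 50% vs 70% | 0.71 | 1.67 |

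In 40,000 simulated trials at 203 per arm (Wald test on the log odds ratio, 0.5 added per cell), the nominal 5% interaction test rejects in 17.9% under the first row. It rejects in 2.6% when the grade depends on the event (30% to 70%) but not on arm.

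**The case against.** The strongest reply is that the damage may be small.

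- **Scale.** The contrast of -1.5 and -5.9 points is a risk-difference effect; the odds ratios are practically equal. Logistic regression would be a usual choice for these binary endpoints, though the plan does not say so. In the step 4 scenario the logistic-type interaction test rejects in about 1.8% of simulated trials, against roughly 13 to 14% on the risk-difference scale, depending on the variance formula. This stands: bias in the odds ratio needs dependence on arm, for which the documents give no evidence either way.
- **Weight.** The section is headed exploratory, and about 15 events are expected. This also stands, and limits the severity. It does not make the comparison valid.
- **Intention to treat.** The plan applies this principle to all efficacy analyses. It fixes the arm but not the subgroup, so it does not answer the point.

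Some stronger readings are tempting but not supported:

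- A reader might infer that the analysis would falsely show prasugrel helping mainly in incompletely occluded aneurysms. If the drug also raised incomplete occlusion by 10 points in step 4, the risk ratios would be 0.46 (incomplete) and 0.38 (complete), which on the ratio scale points the other way. The direction cannot be predicted.
- A reader might infer that the grade always follows the primary event. Events up to Day 30 can come after an end-of-procedure grade.
- A reader might suppose that an operator's reaction to a thrombus changes the grade. That is plausible, but the documents do not describe it.
- A reader might extend the fault to the procedure subgroup and to the stent group named in the size subgroup. The plan does not say whether these follow the planned or the placed device, so this is only a request for clarification.

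**Conclusion.** The point holds in a limited form. That the grade is post-randomisation follows from the documents alone and needs no assumption. Arms within a grade are therefore not a randomised comparison, and the treatment-by-grade interaction does not identify effect modification.

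Whether false modification would appear, on which scale and how large, is conditional. With equal shifts in both arms it is confined in practice to risk differences. On the odds-ratio scale it requires the grade to depend on arm, where the illustrations range from 1.50 and 0.88 to 2.00 and 0.75 for differences of 10 and 20 points without an event. These figures show what can happen; they are not estimates for this trial.

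The primary comparison and the 182 and 203 per group are untouched. This should be corrected, but it does not threaten the trial's main result.

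**What to change.** Remove occlusion grade from the interaction subgroup list. Report it by arm as a descriptive procedural outcome, and state when it is graded. As a clarification only, add that the procedure subgroup and the stent group are formed by the treatment planned at randomisation, which is what the inclusion criterion already refers to.

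The cost is a change of wording in the analysis plan and the loss of one exploratory interaction table. No new data, patients or change to the primary analysis are needed. If the sponsor wishes to keep outcomes tabulated by grade, the table should be labelled non-randomised and descriptive, without an interaction test.
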